12.3 Exclusion criteria

Subjects meeting any of these criteria will not be enrolled in the study:

- 12-leads Electrocardiogram (ECG) (supine position):* clinically significant abnormalities at screening. With regards to QTc, the following will be considered as exclusion criterion: mean corrected QT (QTcF) > 450 ms. HR < 50 or > 99 bpm. PR < 100 or > 220 ms. QRS > 120 ms. Relevantly abnormal T-wave patterns
- Physical examination findings:* clinically significant abnormal physical findings which could interfere with the objectives of the study
- Laboratory analyses:* clinically significant abnormal laboratory values at screening, indicative of physical illness or suggesting the subject's exclusion, in his/her best interest
- Allergy:* ascertained or presumptive hypersensitivity to the active principle and/or formulations' ingredients; history of anaphylaxis to drugs or allergic reactions in general, which the investigator considers may affect the outcome of the study
- Diseases:* significant history, in the opinion of the Investigator, of renal, hepatic, gastrointestinal, cardiovascular (in particular, heart failure, hypokalemia, family history of Long QT Syndrome, history of superficial thrombophlebitis or deep vein thrombosis), respiratory, skin, hematological, endocrine or neurological diseases that may interfere with the aim of the study
- Medications:* medications, including over the counter (OTC) medications and herbal remedies in the 2 weeks before the first visit of the study. Hormonal contraceptives for women are allowed
- CYP3A4 inducers and inhibitors:* use of any inducer or inhibitor of CYP3A4 enzymes (drugs, food, herbal remedies) in the 28 days or in the 7 days, respectively, before the planned first study drug administration and during the whole study
- Investigative drug studies:* participation in the evaluation of any investigational product for 3 months before this study. The 3-month interval is calculated as the time between the first

calendar day of the month that follows the last visit of the previous study and the first day of the present study

9. *Blood donation or significant blood loss*: blood donations or significant blood loss in the 3 months before the first visit of this study
10. *Drug, alcohol, caffeine, tobacco*: history of drug, alcohol [>1 drink/day for women and >2 drinks/day for men, defined according to the USDA Dietary Guidelines 2020-2025 (11)], caffeine (>5 cups coffee/tea/day) or tobacco abuse (≥ 10 cigarettes/day)
11. *Drug test*: positive result at the urine drug screening test at screening or Day -1
12. *Alcohol test*: positive salivary alcohol test at Day -1
13. *Diet*: abnormal diets (<1600 or >3500 kcal/day) or substantial changes in eating habits in the 4 weeks before screening; vegetarians
14. *Pregnancy (women only)*: positive or missing pregnancy test at screening or Day -1, pregnant or lactating women
15. *Netupitant studies*: enrolment in a previous study of netupitant or fosnetupitant (alone or in combination with palonosetron)

12.3.1 Not allowed treatments

No medication, including OTC and herbal remedies, will be allowed in the 2 weeks before the first visit of the study (Screening - Visit 1) and during the whole study duration. In particular, the use of CYP3A4 inducers or CYP3A4 inhibitors (drugs, food, herbs) in the 28 days or in the 7 days, respectively, before the 1st study treatment intake on Day 1 will not be allowed.

Paracetamol will be allowed as therapeutic countermeasure for certain types of AEs according to the Investigator's opinion. Hormonal contraceptives will be allowed.

The intake of any other medication will be reported as a protocol deviation. However, it will lead to subject's discontinuation from the study only if the Investigator, together with the Sponsor, considers the medication as being able to affect the study assessments or outcome.

12.4 Use of contraceptive methods

In case of men or women of childbearing potential, the Investigator, in consultation with the subject, will select the appropriate method/methods of contraception for the individual according to the list of contraception methods of inclusion criteria 6 and 7, and instruct the subject or a screened man referring to his partner in their consistent and correct use. Highly effective contraceptive measures include those listed in inclusion criteria 6 and 7.

Moreover, men will not donate sperm from the date of the informed consent form's signature, throughout the study, and for at least 14 days after the last dose of the study treatment.

At screening and at each study visit, the Investigator will instruct subjects on the need to use contraception throughout the study and to continue for 14 days after the last dose of assigned treatment. In addition, the Investigator will instruct the subjects to call immediately if a selected birth control method is discontinued or if pregnancy is known or suspected.

13 STUDY SCHEDULE

The schedule of the study is summarized in [Table 4.1](#) for study Part A and in [Table 4.2](#) for study Part B.

13.1 Study visits and procedures

Each subject taking part in study Part A will undergo 4 visits, while each subject participating in Part B will undergo 21 visits.

Study **Part A** foresees, after the screening process, a confinement of approximately one and a half days at the Phase I Unit and one ambulatory visit (V4) 7 days post-dose. The maximum study duration for study part A will be 28 days, including the screening period.

Study **Part B** foresees 2 periods separated by a wash-out interval of at least 28 days between the day of T and the day of R treatment administration. After a confinement of approximately 2 and a half days at the Phase I Unit for the treatment with P, the subjects will remain confined for period 1 for approximately 2 further days. Period 2 will consist in a confinement of approximately 3 days at the Phase I Unit. In each period, the confinement will be followed by 8 ambulatory visits, the last of which will be the final visit (Visit 21). The maximum study duration for study Part B will be 62 days, including the screening period (Days -21 to -2) and assuming a 28-day wash-out period between active treatment (T or R) administration days (Day 3 of period 1 and Day 1 of period 2).

The first subject first visit (FSFV) is defined as the 1st screening visit performed at the Phase I Unit for study part A by the 1st screened subject. The last subject last visit (LSLV) is defined as the last visit performed at the Phase I Unit by the last subject in study part B, i.e., the last visit foreseen by the study protocol, independently of the fact that the subject is a completer or a withdrawn subject.

The following parts, phases, visits and procedures will be performed:

- **Part A**
 - **Screening phase**
 - Screening – visit 1: between Day -21 and Day -2
 - Visit 2: Day -1
 - **Interventional phase**
 - Visit 3: Days 1-2
 - **Final phase**
 - Visit 4: Day 7: Final visit or Early termination visit (ETV). In case of early discontinuation, discontinued subjects will undergo an ETV.
- **Part B**
 - **Screening phase**

- Screening – visit 1: between Day -21 and Day -2
- Period 1 – visit 2: Day -1

➤ **Interventional phase**

- Period 1 – visit 3: Days 1-5
- Period 1 – visit 4: Day 6
- Period 1 – visit 5: Day 7
- Period 1 – visit 6: Day 8
- Period 1 – visit 7: Day 9
- Period 1 – visit 8: Day 10
- Period 1 – visit 9: Day 11
- Period 1 – visit 10: Day 12
- Period 1 – visit 11: Day 13
- Wash-out interval of at least 28 days between the 2 administration days of T and R (Day 3 of period 1 and Day 1 of period 2)
- Period 2 – visit 12: Day -1
- Period 2 – visit 13: Days 1-3
- Period 2 – visit 14: Day 4
- Period 2 – visit 15: Day 5
- Period 2 – visit 16: Day 6
- Period 2 – visit 17: Day 7
- Period 2 – visit 18: Day 8
- Period 2 – visit 19: Day 9
- Period 2 – visit 20: Day 10

➤ **Final phase**

- Period 2 – visit 21: Day 11: Final visit or Early termination visit (ETV). In case of early discontinuation, discontinued subjects will undergo an ETV.

Table 13.1.1 Study procedures of Part A

	Day	Procedures/Assessments	Notes
Screening – visit 1	From Day -21 to Day -2	
 ➤ Explanation to the subject of study aims, procedures and possible risks ➤ Informed consent signature ➤ Screening number assignment (as S001, S002, etc.) (§ 20.2) ➤ Demographic data and lifestyle recording ➤ Medical/surgical history ➤ Previous/concomitant medications ➤ Full physical examination (body weight, height, body mass index, vital signs, physical abnormalities) (§ 14.1) ➤ Triplicate 12-lead ECG recording (§14.3.1) ➤ Laboratory analyses: hematology, blood chemistry, urinalysis and virology ➤ Serum pregnancy test (women only) ➤ Urine multi-drug screening test ➤ AE recording ➤ Inclusion/exclusion criteria evaluation 	Note: The first two letters of the surname followed by the first two letters of the first name will be used in the Phase I Unit source document only and will not be transferred to the Sponsor
Visit 2	Day -1	
 ➤ Short physical examination (only if screening physical examination performed more than 7 days before Day -1) (§ 14.1) ➤ Recording of concomitant medications ➤ Salivary alcohol test ➤ Urine pregnancy test (women only) ➤ Urine multi-drug screening test ➤ Body weight (§ 14.1) ➤ Vital signs measurement (§ 14.2) ➤ AE recording ➤ Inclusion/exclusion criteria evaluation ➤ Eligibility evaluation ➤ Enrolment ➤ Subject study number assignment (as 001, 002, etc.) (§ 20.2) 	
Arrival at the Phase I Unit in the evening
 
Confinement until the morning of Day 2
 
Standardized low-fat dinner
 
Fasting for 10 h (overnight)

Visit 3	Day 1	
 ➤ T or Ra treatment ➤ Vital signs measurement (§ 14.2) ➤ Triplicate 12-lead ECG recording (§14.3.1) ➤ Blood sample collection for PK analysis (§ 14.5.1) ➤ Recording of concomitant medications ➤ AE recording 	
Standardized lunch at about 13:00 (5 h post-dose)
 
Standardized dinner at about 20:00 (12 h post-dose)

	Day 2	
 ➤ Vital signs measurement (§ 14.2) ➤ Triplicate 12-lead ECG recording (§14.3.1) ➤ Blood sample collection for PK analysis (§ 14.5.1) ➤ Recording of concomitant medications ➤ Short physical examination upon discharge (§ 14.1) ➤ AE recording 	Discharge from the Phase I Unit in the morning after the 24-h post-dose blood sample collection, ECG recording and vital signs check

	Day	Procedures/Assessments	Notes
Visit 4 - Final Visit/ETV	Day 7 / at ETV in case of discontinuation	
 ➤ Full physical examination (body weight and physical abnormalities) (§ 14.1) ➤ Recording of concomitant medications ➤ Vital signs measurement (§ 14.2) ➤ Triplicate 12-lead ECG recording (§ 14.3.1) ➤ Urine pregnancy test (women only) ➤ Laboratory analyses as at screening, except for virology ➤ AE recording 
In case of clinically significant results at the final visit, the subjects will be followed-up by the Investigator until the normalization of the concerned clinical parameter(s)
	Upon leaving, the subjects will be instructed to contact immediately the Investigator in case of occurrence of any adverse reactions

Table 13.1.2 Study procedures of Part B

	Day	Procedures/Assessments	Notes
Screening – visit 1	From Day -21 to Day -2	
 ➤ Explanation to the subject of study aims, procedures and possible risks ➤ Informed consent signature ➤ Screening number assignment (as S101, S102, etc.) (§ 20.2) ➤ Demographic data and lifestyle recording ➤ Medical/surgical history ➤ Previous/concomitant medications ➤ Full physical examination (body weight, height, body mass index, vital signs, physical abnormalities) (§ 14.1) ➤ Triplicate 12-lead ECG recording (§ 14.3.1) ➤ Laboratory analyses: hematology, blood chemistry, urinalysis and virology ➤ Serum pregnancy test (women only) ➤ Urine multi-drug screening test ➤ AE recording ➤ Inclusion/exclusion criteria evaluation 	Note: The first two letters of the surname followed by the first two letters of the first name will be used in the Phase I Unit source document only and will not be transferred to the Sponsor
Visit 2	Day -1	
 ➤ Short physical examination (only if screening physical examination performed more than 7 days before Day -1) (§ 14.1) ➤ Recording of concomitant medications ➤ Salivary alcohol test ➤ Urine multi-drug screening test ➤ Urine pregnancy test (women only) ➤ Body weight (§ 14.1) ➤ AE recording ➤ Inclusion/exclusion criteria evaluation ➤ Eligibility evaluation ➤ Enrolment and randomization ➤ Subject randomization number assignment (as 101, 102, etc.) (§ 20.2) 	
Arrival at the Phase I Unit in the evening
 
Confinement until the morning of Day 5
 
Standardized low-fat dinner
 
Fasting for 10 h (overnight)

	Day	Procedures/Assessments	Notes
Visit 3	Day 1	
 ➤ P treatment ➤ Vital signs measurement (§ 14.2) ➤ Continuous 12-lead ECG recording (§ Error! Reference source not found.) ➤ Triplicate 12-lead ECG recording (§ 14.3.1) ➤ Recording of concomitant medications ➤ AE recording 	Standardized lunch at about 13:00 (5 h post-dose)
	Day 2	
 ➤ Vital signs measurement (§ 14.2) ➤ Continuous 12-lead ECG recording (§ Error! Reference source not found.) ➤ Triplicate 12-lead ECG recording (§ 14.3.1) ➤ Recording of concomitant medications ➤ AE recording 	Standardized breakfast, lunch and low-fat dinner at about 08:00, 13:00 and 20:00 and then fasting for 10 h (overnight)
	Day 3	
 ➤ T or R treatment ➤ Vital signs measurement (§ 14.2) ➤ Continuous 12-lead ECG recording (§ Error! Reference source not found.) ➤ Triplicate 12-lead ECG recording (§ 14.3.1) ➤ Recording of concomitant medications ➤ Blood sample collection for PK analysis (§ 14.5.1) ➤ AE recording 	Standardized lunch at about 13:00 (5 h post-dose) Standardized dinner at about 20:00 (12 h post-dose)
	Day 4	
 ➤ Vital signs measurement (§ 14.2) ➤ Continuous 12-lead ECG recording (§ Error! Reference source not found.) ➤ Triplicate 12-lead ECG recording (§ 14.3.1) ➤ Recording of concomitant medications ➤ Blood sample collection for PK analysis (§ 14.5.1) ➤ AE recording 	Standardized breakfast, lunch and dinner at about 08:00, 13:00 and 20:00
	Day 5	
 ➤ Vital signs measurement (§ 14.2) ➤ Continuous 12-lead ECG recording (§ Error! Reference source not found.) ➤ Triplicate 12-lead ECG recording (§ 14.3.1) ➤ Recording of concomitant medications ➤ Blood sample collection for PK analysis (§ 14.5.1) ➤ AE recording 	Discharge from the Phase I Unit in the morning after the 48-h post-dose blood sample collection, ECG recording and vital signs check
Visit 4	Day 6	
 ➤ Blood sample collection for PK analysis: 72 h post-dose ➤ Vital signs measurement (§ 14.2) ➤ Recording of concomitant medications ➤ AE recording 	Ambulatory visit. Arrival at the Phase I Unit in the morning.
Visit 5	Day 7	
 ➤ Blood sample collection for PK analysis: 96 h post-dose ➤ Vital signs measurement (§ 14.2) ➤ Recording of concomitant medications ➤ AE recording 	As visit 4

	Day	Procedures/Assessments	Notes
Visit 6	Day 8	
 ➤ Blood sample collection for PK analysis: 120 h post-dose ➤ Vital signs measurement (§ 14.2) ➤ Recording of concomitant medications ➤ AE recording 	As visit 4
Visit 7	Day 9	
 ➤ Blood sample collection for PK analysis: 144 h post-dose ➤ Vital signs measurement (§ 14.2) ➤ Recording of concomitant medications ➤ AE recording 	As visit 4
Visit 8	Day 10	
 ➤ Blood sample collection for PK analysis: 168 h post-dose ➤ Vital signs measurement (§ 14.2) ➤ Recording of concomitant medications ➤ AE recording 	As visit 4
Visit 9	Day 11	
 ➤ Blood sample collection for PK analysis: 192 h post-dose ➤ Vital signs measurement (§ 14.2) ➤ Recording of concomitant medications ➤ AE recording 	As visit 4
Visit 10	Day 12	
 ➤ Blood sample collection for PK analysis: 216 h post-dose ➤ Vital signs measurement (§ 14.2) ➤ Recording of concomitant medications ➤ AE recording 	As visit 4
Visit 11	Day 13	
 ➤ Blood sample collection for PK analysis: 240 h post-dose ➤ Recording of concomitant medications ➤ Short physical examination (§ 14.1) ➤ Laboratory analyses as at screening, with the exception of virology ➤ Vital signs measurement (§ 14.2) ➤ Triplicate 12-lead ECG recording (§ 14.3.1) ➤ Urine pregnancy test (women only) ➤ AE recording 	As visit 4
Wash-out	At least 28 days	A wash-out interval of at least 28 days will elapse between the two administrations of active treatment (T and R) of the two study periods (Day 3 of period 1 and Day 1 of period 2)	
Visit 12	Day -1	
 ➤ Short physical examination (§ 14.1) ➤ Recording of concomitant medications ➤ Salivary alcohol test ➤ Urine multi-drug screening test ➤ Urine pregnancy test (women only) ➤ Body weight (§ 14.1) ➤ Laboratory analyses as at screening, except for virology ➤ AE recording 	As visit 2

	Day	Procedures/Assessments	Notes
Visit 13	Days 1-3	As Days 3-5 of visit 3. T or R treatment according to the randomization list and cross-over design	As Days 3-5 of visit 3
Visit 14	Day 4	
 ➤ Blood sample collection for PK analysis: 72 h post-dose ➤ Vital signs measurement (§ 14.2) ➤ Recording of concomitant medications ➤ AE recording 	Ambulatory visit. Arrival at the Phase I Unit in the morning.
Visit 15	Day 5	
 ➤ Blood sample collection for PK analysis: 96 h post-dose ➤ Vital signs measurement (§ 14.2) ➤ Recording of concomitant medications ➤ AE recording 	As visit 14
Visit 16	Day 6	
 ➤ Blood sample collection for PK analysis: 120 h post-dose ➤ Vital signs measurement (§ 14.2) ➤ Recording of concomitant medications ➤ AE recording 	As visit 14
Visit 17	Day 7	
 ➤ Blood sample collection for PK analysis: 144 h post-dose ➤ Vital signs measurement (§ 14.2) ➤ Recording of concomitant medications ➤ AE recording 	As visit 14
Visit 18	Day 8	
 ➤ Blood sample collection for PK analysis: 168 h post-dose ➤ Vital signs measurement (§ 14.2) ➤ Recording of concomitant medications ➤ AE recording 	As visit 14
Visit 19	Day 9	
 ➤ Blood sample collection for PK analysis: 192 h post-dose ➤ Vital signs measurement (§ 14.2) ➤ Recording of concomitant medications ➤ AE recording 	As visit 14
Visit 20	Day 10	
 ➤ Blood sample collection for PK analysis: 216 h post-dose ➤ Vital signs measurement (§ 14.2) ➤ Recording of concomitant medications ➤ AE recording 	As visit 14

	Day	Procedures/Assessments	Notes
Visit 21 - Final Visit/ETV	Day 11 of period 2 / at ETV in case of discontinuation	
 ➤ Blood sample collection for PK analysis: 240 h post-dose ➤ Laboratory analyses as at screening, except for virology ➤ Vital signs measurement (§ 14.2) ➤ Triplicate 12-lead ECG recording (§14.3.1) ➤ Urine pregnancy test (women only) ➤ Full physical examination (body weight and physical abnormalities) (§ 14.1) ➤ Recording of concomitant medications ➤ AE recording 
In case of clinically significant results at the final visit, the subjects will be followed-up by the Investigator until the normalization of the concerned clinical parameter(s)
	Upon leaving, the subjects will be instructed to contact immediately the Investigator in case of occurrence of any adverse reactions

13.2 Decisional process for escalation to next administration duration

All TEAEs will be recorded in the CRF. TEAEs will be assessed by the Investigator with focus on general safety and local tolerability (i.e., any TEAEs appearing after start of injection and interesting the injection arm).

Following all planned subject's safety assessments and before subject's discharge, the Investigator will evaluate the reported TEAEs.

13.2.1 Decisional process for treatment of subjects within the cohorts

Subjects belonging to cohort 2, 3 and 4 will be sequentially treated as 3 subgroups of 3, 3 and 4 subjects respectively, in each cohort.

Following the treatment of the first 3 subjects in the cohort, the collected safety parameters will be carefully assessed by the Investigator. In particular, the local tolerability will be evaluated in view of confirming the treatment of the next subgroup of 3 subjects in the same cohort. If deemed necessary, the study Investigator will contact the Sponsor Medical Expert and seek advice.

The same process will be repeated following the second subgroup of 3 subjects for confirming the treatment of the last 4 subjects of the cohort.

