Dose regimens: Part A of the study: In cohort 1, 10 healthy volunteers (HV) will receive a dose of T as a one single 30-min IV infusion and additional 10 subjects will receive a single IV dose of undiluted R (treatment Ra) as a one single 30-min IV infusion of 20 mL, according to a parallel group design. In each of 3 consecutive cohorts - 2, 3 and 4, - 10 healthy volunteers (HV) will receive a single IV dose of T and will be sequentially treated as subgroups of 3, 3, and 4 subjects, respectively. A staggered approach with decreasing infusion time duration will be applied to the injection of T in cohorts 2, 3 and 4. Therefore, in each cohort, the T injection duration will vary as follows: Cohort 1: 30 min (T or Ra) Cohort 2: 15 min (T) Cohort 3: 5 min (T) Cohort 4: 2 min (T) At the end of cohort 1 and of each subgroup of cohorts 2, 3 and 4, safety and tolerability results will be evaluated by the Investigator and the study Sponsor Medical Expert. Predefined stopping rules will be considered for deciding about continuing with the next cohort and a shorter injection duration. If the safety data obtained from a treated cohort are considered as not sufficient for taking a decision on the infusion duration de-escalation process and if additional safety data are deemed necessary to allow such decision to be taken, the study Investigator and the Sponsor Medical Expert may decide to add additional subjects (up to a maximum of 4 subjects per cohort) to the 10 subjects of the treated cohort. After cohort 1, if the injection duration of 30 min of T proves to be safe and well tolerated, 15 min will be tested in cohort 2. After cohort 2, if the injection duration of 15 min proves to be safe and well-tolerated, 5 min will be tested in cohort 3. After cohort 3, if the injection duration of 5 min proves to be safe and well-tolerated, 2 min will be tested in cohort 4. At the end of study Part A, the Sponsor will take a final decision whether to proceed with study Part B with the resulting shortest injection duration considered as adequate in terms of safety determined in study Part A. Part B of the study will follow a 2-way, cross-over randomized design and will include 40 male and female subjects. Before entering the crossover phase, each subject will receive P at the shortest infusion duration

STUDY SYNOPSIS (cont.)

Dose regimens (continued):

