13.2.2 Decisional process for escalation to next administration duration

Following the completion of each cohort, the Sponsor Medical Expert will be provided with a summary of the observed tolerability, detailing each TEAE reported up to 60 min after the end of infusion of T and up to subject's discharge on Day 2. The Investigator will provide his assessments on severity and relationship to T. The Investigator will also provide a conclusion on the systemic and local tolerability related to the administration duration of T tested in the cohort, including his suggestion whether to consider safe to proceed with treating the next cohort of subjects with the next predefined infusion duration of T.

If the safety data obtained from a T treated cohort are considered as not sufficient for taking a decision on the infusion duration de-escalation process, and if additional safety data are deemed necessary to allow such decision to be taken, the study Investigator and the Sponsor Medical Expert may decide to add additional subjects (up to a maximum of 4 subjects per cohort) to the 10 subjects of the treated cohort.

The Sponsor Medical Expert will confirm the Sponsor's agreement to proceed or not with the treatment of the next planned subjects' cohort / injection duration.

Study Part A will be stopped if any of the following criteria is met:

1. Any serious adverse event (SAE) assessed as at least possibly related to T experienced within 60 min after the end of T injection by at least one subject in a cohort.
2. Any AE coded with the same preferred term (PT) occurring to 2 subjects of the same cohort with both AEs judged at least as possibly related to T and of severe intensity, within 60 min after the end of T injection.
3. Any AE coded with the same PT occurring to 3 (or more) subjects of the same cohort with the AEs judged at least as possibly related to T and of moderate intensity, within 60 min after the end of T injection.

At the end of study Part A, the Sponsor will take a final decision whether to proceed with study Part B with the resulting shortest injection duration considered as adequate in terms of safety determined in study Part A.

The shortest injection duration selected based on the safety and tolerability results of **Part A**, will be applied in **Part B**.

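### Part A: the protocol disagrees with itself on whether the Sponsor Medical Expert reviews every subgroup, and stopping criterion 3 misses two moderate events plus one severe event

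*Protocol*

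**What the plan says.** **Review after each subgroup.** Section 3, under both the dose regimens and the Part A procedures, calls for a joint evaluation once cohort 1 is complete and also after "each subgroup of cohorts 2, 3 and 4, safety and tolerability results will be evaluated by the Investigator and the study Sponsor Medical Expert". Section 10.1.2 repeats this. No condition is attached.

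Section 13.2.1 describes the step differently. After the first three subjects of a cohort, the Investigator assesses the safety data and confirms whether the next subgroup is treated. Of the expert it says: "If deemed necessary, the study Investigator will contact the Sponsor Medical Expert and seek advice". It continues: "The same process will be repeated following the second subgroup of 3 subjects for confirming the treatment of the last 4 subjects of the cohort". Section 13.2.2 then brings the expert in: "Following the completion of each cohort, the Sponsor Medical Expert will be provided with a summary of the observed tolerability". The expert also confirms the Sponsor's "agreement to proceed or not with the treatment of the next planned" cohort. Section 13.2 keeps one general safeguard: before "discharge, the Investigator will evaluate the reported TEAEs".

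**Stopping criteria (Section 13.2.2).** Any one of three stops Part A:

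- Criterion 1: "Any serious adverse event (SAE) assessed as at least possibly related to T experienced within 60 min after the end of T injection", in at least one subject of a cohort.
- Criterion 2: events of one preferred term "occurring to 2 subjects of the same cohort with both AEs judged at least as possibly related to T and of severe intensity", within the same 60 minutes.
- Criterion 3: events of one preferred term in three or more subjects of a cohort, at least possibly related and graded moderate, within the same 60 minutes.

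Section 18.3.1 defines moderate and severe as separate grades. Section 18.2 defines seriousness by other criteria, such as death, threat to life or hospitalisation, so a severe event need not be serious.

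**The concern.** Staff at the unit will follow Section 13.2.1, because it sets out the procedure. If they do, the next subgroup can be dosed at the same duration before the second reviewer named in Sections 3 and 10.1.2 has seen the data. The protocol's amendment history for version 3.0 says that the Ethics Committee required the subgroups to improve the safety check at infusions shorter than 30 minutes. How strong that check is should not depend on which section is read.

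A mandatory stopping rule should also never become easier to pass as the events get worse. As worded, criterion 3 does: if one of three moderate events is regraded to severe without being serious, the automatic stop disappears.

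The two points can coincide. If the missed pattern is complete by the end of subgroup 1 or 2, no criterion fires, and under Section 13.2.1 the Investigator may decide alone on the next subgroup.

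**Working it through.** The protocol gives no figure to reproduce on this point. The check is a comparison of sections, then an exact enumeration.

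**1. Who reviews, and when (each of cohorts 2, 3 and 4)**

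| Point | Sections 3 and 10.1.2 | Sections 13.2.1 and 13.2.2 |
|---|---|---|
| After subgroup 1 (3 subjects) | Investigator and expert | Investigator; expert optional |
| After subgroup 2 (3 subjects) | Investigator and expert | Investigator; expert optional |
| After subgroup 3 (4 subjects, cohort complete) | Investigator and expert | Investigator and expert |

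Subgroup ends: 3 cohorts × 3 = 9. Expert optional under Section 13.2.1: 3 × 2 = 6. Expert provided for: 3 × 1 = 3. The three moves to a shorter duration (30 to 15, 15 to 5, 5 to 2 min) are unaffected.

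Reading Sections 3 and 10.1.2 as meaning cohort end only does not reconcile the texts, because their explicit mention of each subgroup would then have no effect.

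**2. Patterns the stopping rules catch**

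For one preferred term in one cohort, counting only events at least possibly related and within 60 minutes, let m be the number of subjects with a moderate event, s the number with a severe event, and k the number of these events that are serious. Criterion 2 is taken to mean two or more severe events.

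- Rule as written: stop if k ≥ 1, or s ≥ 2, or m ≥ 3.
- Rule with criterion 3 extended upward: stop if k ≥ 1, or s ≥ 2, or m + s ≥ 3.

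The written rule fails to stop only when k = 0, s is 0 or 1, and m is 0, 1 or 2, which is six patterns. Of those six, m + s reaches 3 only at m = 2, s = 1. That is the whole gap, whatever the cohort size.

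| Three affected subjects, none serious | As written | Extended |
|---|---|---|
| 3 moderate | stop | stop |
| 2 moderate + 1 severe | **no stop** | stop |
| 1 moderate + 2 severe | stop | stop |
| 3 severe | stop | stop |

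If any of the events is serious, criterion 1 stops Part A under both rules. Non-serious patterns stopped, as written against extended:

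- 3 subjects: 4 against 5 of 10
- 6 subjects: 22 against 23 of 28
- 10 subjects: 60 against 61 of 66
- 14 subjects (10 plus the permitted 4): 114 against 115 of 120

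These are counts of patterns, not probabilities.

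**3. How often it could matter (assumed rates, not from the protocol)**

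With per-subject probabilities p of a moderate and q of a severe non-serious event of one preferred term, the chance of the missed pattern in 10 subjects is 10!/(2! 1! 7!) × p² × q × (1 − p − q)⁷ = 360 p² q (1 − p − q)⁷.

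| p / q | Stop as written | Stop extended | Difference (points) |
|---|---|---|---|
| 10% / 2% | 8.6% | 11.5% | 2.9 |
| 10% / 5% | 15.3% | 21.1% | 5.8 |
| 20% / 5% | 39.0% | 48.6% | 9.6 |
| 20% / 10% | 52.5% | 64.3% | 11.9 |
| 30% / 10% | 75.0% | 84.0% | 9.1 |

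The chance that the pattern is complete within the first subgroup of three is 3 p² q. That is 3 × 0.01 × 0.02 = 0.06% at 10%/2%, and 3 × 0.04 × 0.10 = 1.2% at 20%/10%.

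**The case against.** **On the review.** Sections 3 and 10.1.2 place the joint evaluation at the end of each subgroup but do not say that dosing must wait for it. Their next sentence links the stopping rules to the next cohort, where the expert's agreement is always needed. Section 13.2.2 does not forbid sharing data earlier, so the sections could be read cumulatively: joint evaluation of each subgroup, with the Investigator releasing the next one. The amendment history calls for sequential subgroups, not for clearance of each by the expert, so Sections 3 and 10.1.2 could instead be relaxed. The point about timing stands, and the fix therefore has to state it. The cumulative reading does not sit with Section 13.2.1, which leaves contacting the expert to the Investigator's judgement. Relaxing the other sections would remove the inconsistency but would weaken a check the Ethics Committee wanted improved.

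**On criterion 3.** A sensible reader would count a severe event towards a rule that three moderate events trigger. Some severe events would also be serious and fall under criterion 1, since Section 18.2 includes events judged medically important. Section 19.2 lets the Investigator or the Sponsor stop the study at any time for medical reasons. All this limits the practical effect. But in criterion 3 the wording for a minimum level attaches to relatedness, not to intensity, and a mandatory stop should not rest on a generous reading.

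**On the overlap.** It needs three affected subjects among the first three or six, and an Investigator who neither pauses nor seeks advice. That is unlikely and adds little weight.

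**Conclusion.** Both points hold and should be corrected. The sections conflict on who reviews the data at 6 of the 9 subgroup ends in cohorts 2 to 4. Criterion 3 misses exactly one pattern: two moderate events and one severe, non-serious event of the same preferred term. The second conclusion rests on the literal wording of criterion 3, on criterion 2 meaning two or more, and on severe events that are not serious; the percentages above rest on assumed event rates.

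The consequence is bounded. The Investigator reviews every subgroup, no shorter duration is reached without the expert, and discretionary stopping remains. The Part B equivalence analysis is not touched.

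**What to change.** 1. In Section 13.2.1, replace the discretionary contact with a joint evaluation by the Investigator and the Sponsor Medical Expert after subgroups 1 and 2, completed before the next subgroup is dosed. State that timing in Sections 3 and 10.1.2 as well, since neither does so now.
2. In criterion 3 of Section 13.2.2, require *at least moderate* intensity instead of moderate intensity.
3. Optionally, add *or more* after the two subjects in criterion 2. This is clarification only.

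The cost is protocol wording. No subjects or procedures are added. The expert takes part in six within-cohort reviews that Sections 3 and 10.1.2 already describe.
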